Specific Aim 1: To determine the prevalence of *APOL1* renal risk variants among 2,600 HIV-positive individuals in Nigeria and assess whether *APOL1* HR status correlates with prevalent albuminuria, eGFR, and/or prevalent CKD (defined as macroalbuminuria or eGFR <60 ml/min/1.73 m²) in this population.

Hypothesis: ~25% of those screened will carry the *APOL1* HR genotype, which will be associated with albuminuria, lower baseline eGFR, higher uACR, and higher rates of prevalent CKD.

Definitions: Microalbuminuria will be defined as having a mean uACR of 30-300 mg/g. CKD will be defined by the presence of proteinuria or an eGFR of < 60 ml/min/1.73m².

Study Population: We will determine the prevalence of *APOL1* risk variants in a large group of HIV-positive adults (n = 2,600) in Nigeria and correlate them with early markers of kidney disease; namely microalbuminuria, reduced eGFR, and CKD. All consecutively seen HIV-positive ART-experienced (6+ months) adults (\geq 18-70 years of age) presenting for care at AKTH will be approached for enrolment into this study. **NOTE**: We will be enrolling ART-experienced adults (on ART for 6+ months). Specifically, if on ART for 6-12 months, then subjects need to have a plasma viral load value < 20 copies/mL from their 6-month blood draw, and if on ART for > 12 months, then enrolled participants need to have a suppressed viral load result (i.e. < 20 copies/mL) on their most recent viral load blood draw---which needs to be within the past 6 months). Routine viral load monitoring has only recently been implemented at our study site in north-central Nigeria, and by enrolling only patients with recent evidence of viral suppression, we will do our best to eliminate ongoing HIV-associated viral replication in non-adherent persons as a potential contributing cause to immune activation and therefore NCD end-organ complications, including kidney disease.

1.2 Specific Aim 2

Specific Aim 2: To assess whether RAAS inhibition with an ACEi compared to placebo, significantly reduces incidence of albuminuria or reduced eGFR among 280 HIV-positive individuals with microalbuminuria who are receiving ART.

Hypothesis: After two years,

- A significantly higher proportion of participants in the intervention vs. SOC arm will regress from microalbuminuria to normoalbuminuria (uACR<30 mg/g); anticipated hazard ratio = 2.5.

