- Significantly higher proportions of participants in the SOC arm (60% vs. 25% in the intervention arm) will progress from microalbuminuria to macroalbuminuria (uACR>300 mg/g).
- Albuminuria will fall by an average of 40% in the intervention arm and increase by an average of 10% in the SOC arm.

Study population: All HIV-positive ART-experienced (6+ months) screened individuals (n = 2,600) found to have i) confirmed microalbuminuria (mean uACR between 30-300 mg/d obtained at 2 separate measurements at least 4 and no more than 8 weeks apart), (NOTE: based on variability of individual uACR measurements, we also plan to call back Aim 1 participants having normoalbuminuria (especially those with an average uACR value in the 20-29 mg/g range) as well as Aim 1 participants having macroalbuminuria), and ii) fairly well-preserved renal function, namely an eGFR > 60 ml/min/1.73m²; will be approached for enrollment into this study. Based on recent studies at AKTH among HIV positive adults, we anticipate that a minimum of 18% of screened patients (n~460) will be eligible. Therefore, with a target sample size equal to

280 (see Section 10.0), 59% of eligible patients would need to consent for this Aim 2 study.

Primary Endpoints:

- i) Regression from microalbuminuria (uACR=30-300 mg/g) to normoalbuminuria (uACR < 30 mg/g)
- ii) Progression from microalbuminuria (uACR=30-300 mg/g) to macroalbuminuria (uACR > 300 mg/g) by study arm
- iii) Mean change in uACR

Secondary Endpoints:

i) Doubling of serum creatinine from baseline; ii) All-cause mortality (**NOTE**: Planned follow-up is two years for all participants), iii) Proportion experiencing a 40% decline in eGFR (using CKD-EPI-Cr-CyC equation), iv) Mean change in eGFR over time (using CKD-EPI-Cr-CyC equation), and v) change in clinical/performance status (as ascertained via two measures, specifically the WHO quality of life (WHOQOL-HIV) tool (31 questions)^{107,108} and the Karnofsky performance score)¹⁰⁹.

1.3 Specific Aim 3

Specific Aim 3: To determine whether the *APOL1* HR genotype is associated with worse longitudinal kidney outcomes among HIV-positive Nigerians with prevalent albuminuria, with regard to progression of albuminuria and eGFR decline.

Hypothesis: After two years of follow-up, independent of baseline uACR, eGFR, and/or treatment assignment:

- Study participants with the HR genotype will have a more rapid kidney function decline (median eGFR change) compared to those with the LR genotype.

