- Study participants with the LR genotype will have 30% lower mean uACR values (compared to baseline) compared to study participants with the HR genotype.

Study population: All enrolled Aim 2 study participants who completed the study, namely, two years of study follow-up. However, to improve our power to evaluate the influence of *APOL1* risk allele status on key renal outcomes, we will include all enrolled Aim 2 study participants that completed a minimum of one year of clinical follow-up, meaning that if they were lost to follow-up after completing their one-year study visit, we will include them in our Aim 3 genetics outcome analyses.

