Longitudinal Study Assessments: All enrolled patients will undergo the following tests at baseline and then every 3 months while on study, until completing 2 years of followup: serum cystatin C, blood pressure, serum electrolytes (creatinine, potassium, sodium, chloride, bicarbonate, and urea), and uACR. Clinical performance status (as measured via the WHOQOL-HIV tool and the Karnofsky performance score) will be evaluated at baseline and at 12 and 24 months. If participant is a female with reproductive potential, she will undergo urine pregnancy testing every 3 months (please see below in **NOTE**). All enrolled aim 2 study participants will have their APOL1 genotype data (i.e. whether HR or LR genotype) available prior to completing study follow-up (see Study Timeline). All patients will undergo routine standard laboratory monitoring as per existing guidelines; specifically, CD4+ cell count and viral load testing (q 6 monthly), liver function test monitoring (at month 1, 3, and 6, and then q 6 monthly following ART initiation), etc., as per Nigeria standard of care (SOC). All enrolled patients will undergo a blood pressure check and have serum electrolytes tested at week 1 and month 1 following study initiation and any changes in dose as part of a brief safety check. All enrolled patients will undergo hepatitis B and C screening at baseline. Additional funds have been allocated for patients to undergo unscheduled safety monitoring (up to two additional times per year) as needed, while on study.

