6.0 Study Safety Monitoring Plan

Study participants will be recruited and consented at AKTH, Kano, Nigeria. Adherence to human subject regulations will primarily be the responsibility of the Multiple PIs. The study team will adhere to all requirements by: (i) developing a study protocol that is able to meet its stated research objectives, and thus reflect adequate risk-benefit ratios for human subjects; (ii) specifying study procedures in the protocol that protect the rights and safety of human subjects; (iii) developing a recruitment script and informed consent forms that include all elements of consent required by Federal regulations and accurately represents study requirements, risks, and benefits in language that is understandable to study participants, including human subject considerations; and (iv) monitoring adherence to protocol specifications and human subject requirements. The consent forms, protocol, and any subsequent modifications will be reviewed and approved by the Institutional Review Boards (IRB) at Vanderbilt University (FWA00005756), and AKTH (FWA00010841).

A. Adverse Event (AE) Assessment

1. Anticipated risks

Risks that are expected/anticipated as part of participation in the study are detailed in the study information and consent forms that will be distributed to and reviewed with patients by trained study team members. These risks are described below, along with steps that will be taken to minimize these risks:

Risks of blood draws: As described in Study Procedures (Section 6.0), blood specimens will be collected from each participant by routine venipuncture. The risks of venipuncture include discomfort at the site of puncture; possible bruising and swelling around the puncture site; and rarely an infection. We expect no additional psychological or social harms to occur. Other risks may include pain, bleeding, or bruising where the needle enters the skin; lightheadedness; and in rare cases, fainting or infection. These risks will be minimized by hiring study staff who are well trained in phlebotomy and other clinical procedures.

Risks of study medication (lisinopril and losartan)

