Statistical analysis plan: Our first approach will be to perform an intent-to-treat analysis, but we will also perform an on-treatment analysis to compare these data and present all available findings. *Primary analysis*: We will test the hypotheses that regression and progression rates are different across arms using multivariable Cox regression models with the intervention variable (randomization to RAAS [yes/no]) as the primary predictor variable, adjusting for baseline (pre-randomization) covariates including baseline uACR, *APOL1* renal risk variants, CD4+ cell count, blood pressure

ART regimen (DTG vs. other), and the presence/absence of comorbid medical conditions (hypertension, cardiovascular disease). To relax linearity assumptions, baseline uACR will be included in models using restricted cubic splines.¹³⁸ Primary analyses will be intention to treat, although we also plan to perform "per protocol" analysis. We will also test the impact of study arm on uACR using a linear mixed effects model to account for within patient correlation with the outcome of 3-monthly uACR values (with primary endpoints obtained by evaluating the uACR and other key renal outcomes at 18 and 30 months given that all enrolled study participants will not be placed or sustained on their maximum tolerated lisinopril dose or matched placebo until 6 months after study enrollment). The model will also adjust for the baseline covariates given above. For this analysis, we anticipate log-transforming uACR to meet modelling assumptions, although other transformations will be considered if needed.

Secondary analyses: Analyses for secondary endpoints will be similar to that described above. Time-to-event outcomes (doubling of serum creatinine from baseline, all-cause mortality, 40% decline in eGFR, and tenofovir toxicity) will be assessed using multivariable Cox regression models. Continuous outcomes (eGFR, quality of life metrics, and blood pressure) will be analyzed using mixed effects models after proper transformation of the outcome variable, if necessary. Baseline covariates listed above will be included in all secondary analyses.

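### The mixed-model uACR primary endpoint is to be read at 18 and 30 months, but uACR is scheduled only to month 24, and the year-2 point that the hypothesis and evaluable sample use is not named

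*Combined protocol and SAP*

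**What the plan says.** The analysis plan for Specific Aim 2 (section 8.0) fits a linear mixed model to the 3-monthly uACR values, "with primary endpoints obtained by evaluating the uACR and other key renal outcomes at 18 and 30 months". Its reason is that participants will not be settled on their highest tolerated dose, or matched placebo, until 6 months after enrollment. The other key renal outcomes are not listed.

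The rest of the protocol works to two years:

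- **Hypothesis (section 1.2).** The Aim 2 hypotheses open with "Hypothesis: After two years". The uACR hypothesis is "Albuminuria will fall by an average of 40% in the intervention arm and increase by an average of 10% in the SOC arm".
- **Follow-up (section 1.2, secondary endpoints).** "Planned follow-up is two years for all participants".
- **Completion (section 1.3).** The Aim 3 population is "All enrolled Aim 2 study participants who completed the study, namely, two years of study follow-up", with a stated allowance for people lost after the one-year visit.
- **Visit schedule (section 5.0, Longitudinal Study Assessments).** uACR is measured at baseline and then "every 3 months while on study, until completing 2 years of followup". In the same paragraph, quality of life and performance status "will be evaluated at baseline and at 12 and 24 months".
- **Sample size (section 8.0).** The 252 evaluable participants (126 per arm) are those left after 10% loss at the end of year 2.
- **Section 9.0.** Two years of follow-up per participant is repeated.

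**The concern.** A timepoint stated for a primary endpoint falls six months after the last scheduled measurement. If the plan is followed as written, there is no month-30 uACR to analyse. A model with time as a continuous trend would return a month-30 estimate only by projecting past its data. A model with visit as a categorical factor would return none.

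The sentence also leaves out month 24, where the hypothesis and the evaluable sample sit, and it does not say whether month 18 or month 30 decides the endpoint. The 5%/3 split of the type I error counts endpoints, not timepoints within one endpoint. Someone must therefore choose between 18 months, 24 months and a modelled 30 months. If that choice is made after unblinding, it could follow the result. Because the other key renal outcomes are not named, it is unclear how many further analyses inherit the problem.

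**Working it through.** **1. Schedule against analysis timepoints.** Inputs: uACR every 3 months from baseline for two years (section 5.0); analysis at 18 and 30 months, with 6 months to settle the dose (section 8.0).

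Post-baseline uACR visits: 24 / 3 = 8, at months 3, 6, 9, 12, 15, 18, 21 and 24.

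| Month | uACR scheduled | Named in the mixed-model sentence | Months after the 6-month titration |
|---|---|---|---|
| 18 | yes | yes | 18 − 6 = 12 |
| 24 | yes | no | 24 − 6 = 18 |
| 30 | no | yes | 30 − 6 = 24 |

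The named timepoints equal 6 + 12 and 6 + 24, so the authors may have meant 12 and 24 months after titration. No section starts the two years there. The schedule in section 5.0 is stated from baseline, and its quality-of-life assessments are at 12 and 24 months, not 18 and 30.

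**2. Contact after the study.** Section 6.0 provides adverse-event follow-up after completion: 3 months of capture, and open-ended follow-up of unresolved events. It schedules no uACR.

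**3. The plan's own Aim 2C figure.** Inputs: 280 randomized 1:1, 10% loss at the end of year 2, type I error 0.017, 80% power, one final measurement per person (section 8.0); SD of log uACR 0.58 (Appendix B, Table S1). Sidedness is not stated; two-sided reproduces the figure.

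- Evaluable: 280 × 0.90 = 252, or 126 per arm.
- Detectable difference: (z(1 − 0.017/2) + z(0.80)) × √(2/126) = 0.407 SD.
- In log units: 0.407 × 0.58 = 0.236.

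These agree with the stated 0.41 SD and 0.24. Power at 0.24 is 81.5%. The calculation uses year-2 retention, so it already covers a 24-month contrast.

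**4. What 30 months would involve.** Upper bounds, without loss:

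- Visits at months 27 and 30: 280 × 2 = 560.
- Study drug or placebo: 280 × 6 = 1,680 participant-months.

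The documents give no loss figure for month 30, so these cases are assumptions:

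| Assumed loss at month 30 | Per arm | Detectable log difference | Power at 0.24 |
|---|---|---|---|
| 10% (no loss after month 24) | 126 | 0.236 | 81.5% |
| 12.3% (constant rate: 1 − 0.9^(30/24)) | 122.7 | 0.239 | 80.4% |
| 15% | 119 | 0.243 | 79.0% |

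At the constant rate, the extra visits would be 280 × (0.9^(27/24) + 0.9^(30/24)) = 494.

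**The case against.** The strongest reply is that the sentence explains itself: 18 and 30 months are one and two years after titration, and several of the two-year statements give a duration without a starting point. In addition, the shading of the Appendix A timeline, which has a row for Aim 2 follow-up visits, cannot be read in the text reviewed. The intent may well be as described. However, section 5.0 ties the schedule to baseline, and no section moves the clock. Appendix A is a study calendar in 6-month columns. It might show room for longer follow-up, but it could not schedule a participant's month-30 uACR.

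Second, the model uses all the 3-monthly values, so an effect of study arm can be estimated from months 3 to 24 on any reading. That is correct. Only the month-30 read-out fails, but it is one of the two that the plan names.

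Third, the power calculation does not date its final measurement, and its SD comes from the 30-300 mg/g entry range. This also stands. The link to month 24 is the year-2 retention figure, and the same calculation would serve any final visit with about 126 per arm.

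Fourth, the cost of 30 months depends on an intention that the documents do not settle, and loss could exceed 15%. At an assumed 20% (112 per arm), power at 0.24 would be 76.1%.

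Finally, the effect is confined and the repair may be only wording. That limits the cost of correction. It does not make the stated timepoint usable.

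**Conclusion.** The concern holds. As written, one of the two timepoints for the mixed-model uACR primary endpoint lies outside the measurement schedule, and the analysis does not name the year-2 point on which the hypothesis and the evaluable sample rest. The conclusion rests on the written schedule, counted from baseline.

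The scope is limited to the uACR endpoint (Aim 2C) and the unnamed other key renal outcomes. Month 18 is valid, the Cox analyses of regression and progression are not blocked, and the stated Aim 2C power is unaffected. The correction is still needed before unblinding, because the plan otherwise leaves the deciding timepoint of a primary endpoint open.

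**What to change.** Before unblinding, reconcile the mixed-model sentence in section 8.0 with the follow-up and schedule in sections 1.2, 1.3, 5.0 and 9.0 and with the sample size text in section 8.0.

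**If two years stands.** Name one primary uACR contrast that the schedule supplies. The natural choice is the baseline-adjusted treatment difference in log uACR at 24 months, tested at 1.7%, with 18 months supportive. A pre-specified average over post-titration visits within the schedule would also remove the conflict. Estimate it without extrapolating past the last visit; visit as a categorical factor is one suitable way. State that month 24 is about 18 months after the end of titration, and list the other renal outcomes that use the timepoint. The cost is SAP wording only.

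**If 30 months was intended.** Bring the follow-up length, visit schedule, study-drug and safety-laboratory provision and loss allowance into line. Against the schedule as written, this adds at most 560 participant-visits and 1,680 participant-months of study drug or placebo, with the accompanying safety tests. The protocol and consent would need review, since section 6.0 requires that "any subsequent modifications will be reviewed and approved by the Institutional Review Boards".

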cause mortality, and tenofovir toxicity because the expected rates for these events in the placebo arm are anticipated to be small (i.e., 2-20%, <10%, and 2%, respectively). We should have sufficient power to detect meaningful differences in eGFR, quality of life scores, and blood pressure.

alpha	Events Needed	Approx Rate SOC	Approx Rate Exp	Patients per Arm	Power
0.010	38	0.12	0.3	100	0.595
0.010	50	0.16	0.4	100	0.751
0.010	45	0.12	0.3	120	0.695
0.010	60	0.16	0.4	120	0.838
0.010	53	0.12	0.3	140	0.775
0.010	71	0.16	0.4	140	0.898
0.010	60	0.12	0.3	160	0.838
0.010	81	0.16	0.4	160	0.938
0.010	68	0.12	0.3	180	0.886
0.010	91	0.16	0.4	180	0.963
0.017	38	0.12	0.3	100	0.666
0.017	50	0.16	0.4	100	0.807
0.017	45	0.12	0.3	120	0.758
0.017	60	0.16	0.4	120	0.880
0.017	53	0.12	0.3	140	0.828
0.017	71	0.16	0.4	140	0.928
0.017	60	0.12	0.3	160	0.880
0.017	81	0.16	0.4	160	0.958
0.017	68	0.12	0.3	180	0.918
0.017	91	0.16	0.4	180	0.976
0.025	38	0.12	0.3	100	0.717
0.025	50	0.16	0.4	100	0.844
0.025	45	0.12	0.3	120	0.801
0.025	60	0.16	0.4	120	0.907
0.025	53	0.12	0.3	140	0.862
0.025	71	0.16	0.4	140	0.946
0.025	60	0.12	0.3	160	0.907
0.025	81	0.16	0.4	160	0.969
0.025	68	0.12	0.3	180	0.938
0.025	91	0.16	0.4	180	0.983
0.050	38	0.12	0.3	100	0.804
0.050	50	0.16	0.4	100	0.902
0.050	45	0.12	0.3	120	0.870
0.050	60	0.16	0.4	120	0.946
0.050	53	0.12	0.3	140	0.915
0.050	71	0.16	0.4	140	0.971
0.050	60	0.12	0.3	160	0.946
0.050	81	0.16	0.4	160	0.984
0.050	68	0.12	0.3	180	0.966
0.050	91	0.16	0.4	180	0.992

Table 3. Power calculation for regression

For these calculations, an HR of 2.5 was assumed.

Table 4. Detectable hazard ratios (HR) for regression

alpha	Events	Approx	Approx	Patients	Detectable
	Needed	Rate SOC	Rate Exp	per Arm	HR
0.010	42	0.12	0.35	100	2.88
0.010	52	0.16	0.41	100	2.59
0.010	48	0.12	0.32	120	2.69
0.010	59	0.16	0.39	120	2.43
0.010	54	0.12	0.31	140	2.54
0.010	67	0.16	0.37	140	2.31
0.010	59	0.12	0.29	160	2.43
0.010	74	0.16	0.35	160	2.21
0.010	65	0.12	0.28	180	2.34
0.010	81	0.16	0.34	180	2.13
0.017	41	0.12	0.33	100	2.76
0.017	50	0.16	0.40	100	2.49
0.017	46	0.12	0.31	120	2.58
0.017	58	0.16	0.37	120	2.34
0.017	52	0.12	0.29	140	2.45
0.017	65	0.16	0.36	140	2.23
0.017	58	0.12	0.28	160	2.34
0.017	72	0.16	0.34	160	2.14
0.017	63	0.12	0.27	180	2.25
0.017	79	0.16	0.33	180	2.06
0.025	40	0.12	0.32	100	2.66
0.025	49	0.16	0.39	100	2.41
0.025	45	0.12	0.30	120	2.50
0.025	57	0.16	0.36	120	2.27
0.025	51	0.12	0.28	140	2.37
0.025	64	0.16	0.35	140	2.16
0.025	57	0.12	0.27	160	2.27

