Appendix B. Supplemental tables - Statistical calculations for secondary endpoints

Table S1. Detectable differences in means of log-transformed uACR values. The outcome is uACR measurement (units= mg/g) and a t-test will be used to compare the two means of log-transformed uACR for the two arms after follow-up. Given the inclusion criteria with the uACR range of 30-300 mg/g, we assume the log-transformed uACR has

a 95% probability interval from 3.4 to 5.7 and a standard deviation of 0.58. With 90 subjects at the end of study after adjustment for 10% loss to follow up (LTFU), we will have 80% power to detect a difference of 0.42 units of standard deviation (0.24 on log-transformed means assuming standard deviation of 0.58).

,		
alpha	Subjects per	Detectable
	Arm	Difference
0.010	100	0.30
0.010	120	0.27
0.010	140	0.25
0.010	160	0.23
0.010	180	0.22
0.017	100	0.28
0.017	120	0.25
0.017	140	0.24
0.017	160	0.22
0.017	180	0.21
0.025	100	0.27
0.025	120	0.24
0.025	140	0.23
0.025	160	0.21
0.025	180	0.20
0.050	100	0.24
0.050	120	0.22
0.050	140	0.20
0.050	160	0.19
0.050	180	0.18

Table S2. Detectable differences in doubling of serum creatinine. Assuming 2% - 20% of subjects in the SOC arm will be doubling of serum creatinine, we will use an uncorrected chi-squared test to detect the difference between the two arms. In case of 10% of subjects on the SOC arm will have their serum creatinine doubled after follow up, we will have 80% power to detect a 9.3% decrease on the experimental arm to 0.7% (RR=0.07).

Alpha	Rate SOC	Detectable	Rate Exp
	arm	RR	arm
0.01	0.10	0.050	0.005
0.01	0.15	0.193	0.029
0.01	0.20	0.290	0.058
0.05	0.10	0.180	0.018
0.05	0.15	0.307	0.046
0.05	0.20	0.395	0.079

Table S3. All-cause mortality. With 140 patients on each arm, we will have 126 patients on each arm at the end of study assuming 10% LTFU. An uncorrected chi-square test will be used to test the difference of the all-cause mortality between the two arms. In case of the all-cause mortality is 10% on the SOC arm, we will have 80% power to detect an absolute 8.2% decrease on the treatment arm to 1.8%.

Rate of SOC	Power	Detectable Difference	RR	Detectable Rate Exp Arm
0.08	0.8	0.072	0.10	0.008
0.08	0.9	0.079	0.01	0.001
0.10	0.8	0.082	0.18	0.018
0.10	0.9	0.091	0.09	0.009
0.12	0.8	0.092	0.23	0.028
0.12	0.9	0.102	0.15	0.018
0.14	0.8	0.100	0.29	0.040
0.14	0.9	0.112	0.20	0.028
0.16	0.8	0.108	0.32	0.052
0.16	0.9	0.121	0.24	0.039
0.18	0.8	0.115	0.36	0.065
0.18	0.9	0.129	0.28	0.051

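### At about 2% event rates the mandatory full-covariate Cox model has roughly 5 events for 9–13 parameters, and the plan names no sparse-event alternative

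*Combined protocol and SAP*

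**What the plan says.** The secondary-analysis paragraph of Section 8.0 (Specific Aim 2) assigns four outcomes to one method: "doubling of serum creatinine from baseline, all-cause mortality, 40% decline in eGFR, and tenofovir toxicity) will be assessed using multivariable Cox regression models". It leaves no choice of covariates: "Baseline covariates listed above will be included in all secondary analyses". The list comes from the primary-analysis paragraph just before it. It opens with uACR at baseline, APOL1 genotype, the CD4+ count and a blood pressure term, and the remaining entries are given as "ART regimen (DTG vs. other), and the presence/absence of comorbid medical conditions (hypertension, cardiovascular disease"). On functional form, "baseline uACR will be included in models using restricted cubic splines"; the number of knots is not given.

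The sample size text in the same section concedes low power for creatinine doubling, mortality and tenofovir toxicity because "expected rates for these events in the placebo arm are anticipated to be small (i.e., 2-20%, <10%, and 2%, respectively"). Table S2 in Appendix B repeats the creatinine range: "Assuming 2% - 20% of subjects in the SOC arm will be doubling of serum creatinine". Table S4 tabulates 40% eGFR decline at 20–60% in the control arm, with 50% vs 33% as its worked example.

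The plan gives no reduced model, penalised likelihood or exact method for sparse events. Tables S2 and S3 size creatinine doubling and mortality with an uncorrected chi-squared test, not with the adjusted Cox model.

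**The concern.** A Cox model with more parameters than events cannot be expected to give finite estimates for all of them. If no event, or every event, falls in one level of a binary covariate, the partial likelihood has no maximum and that coefficient runs to infinity. The plan fixes the full list for every secondary endpoint, so at its lowest expected rates it prescribes a model that the data cannot support.

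These are the mortality and kidney-safety comparisons. If the prescribed model fails, someone must choose another after seeing the data, and the plan does not say which. The dolutegravir sensitivity analyses in Section 8.0 repeat the secondary models with a time-varying term and then an interaction, so they inherit the problem with one or two more parameters.

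**Working it through.** **Inputs.** From Section 8.0: 280 randomised 1:1, and 126 per arm after 10% loss. From Section 8.0 and Appendix B: the event rates below. Assumed, because the plan does not say: 3–5 spline knots (2–4 terms), APOL1 as 1–2 terms, blood pressure as 1–2 terms.

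**Reproducing the plan's figures.** With n = 126 per arm and two-sided alpha 0.05:

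power = Φ{[|p1 − p2|√n − 1.96√(2p̄(1 − p̄))] / √(p1(1 − p1) + p2(1 − p2))}

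- Table S7, 2% vs 11%: (0.09 × 11.225 − 1.96 × 0.3486)/0.3428 = 0.954, so power is 0.830 (stated 83%).
- Table S7, 2% vs 0.1%: (0.019 × 11.225 − 1.96 × 0.1442)/0.1435 = −0.483, so power is 0.315 (stated 31%).
- Table S3, 10% vs 1.8%: 0.792 (stated 80%).

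The plan's rates and denominators are therefore read correctly.

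**Parameters.** Treatment 1 + uACR 2–4 + APOL1 1–2 + CD4+ 1 + blood pressure 1–2 + ART regimen 1 + hypertension 1 + cardiovascular disease 1 = 9 to 13.

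**Events per parameter.** Events = 126 × (control rate + active rate).

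| Endpoint and rates (control/active) | Events | Per parameter (9 to 13) |
|---|---|---|
| Tenofovir toxicity or creatinine doubling, 2%/2% | 5.0 | 0.56–0.39 |
| Tenofovir toxicity, 2%/0.1% (Table S7) | 2.6 | 0.29–0.20 |
| Tenofovir toxicity, 2%/11% (Table S7) | 16.4 | 1.8–1.3 |
| Mortality, 10%/1.8% (Table S3) | 14.9 | 1.7–1.1 |
| Mortality, 10%/10% | 25.2 | 2.8–1.9 |
| Creatinine doubling, 20%/20% | 50.4 | 5.6–3.9 |
| 40% eGFR decline, 20%/8% (Table S4) | 35.3 | 3.9–2.7 |
| 40% eGFR decline, 50%/33% (Table S4) | 104.6 | 11.6–8.0 |

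**Does the model fail?** Trials were simulated with 140 per arm, 24 months and 10% loss. Infinite coefficients were detected by a linear-programming check. The covariate prevalences are assumptions: cardiovascular disease 5–20%, hypertension 25–40%, dolutegravir 50%. The last column is a separate 9-parameter simulation of 280 patients, also with assumed prevalences, that counted diverging coefficients.

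| Rates | Any coefficient infinite (9–13 parameters) | Treatment infinite (9–13 parameters) | Separate run, 9 parameters: any / treatment |
|---|---|---|---|
| 2%/2% | 55–90% | 11–26% | 78% / 8% |
| 5%/5% | 11–61% | 0–0.7% | 34% / 0.2% |
| 10%/1.8% | 15–57% | 9–13% | 34% / 10% |
| 10%/10% | 1–29% | 0% | 8% / 0% |

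In the separate run the treatment estimate varied about 23% more than the unadjusted one at 2%, and about 5% more from 5% upward.

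**Where the infinite treatment hazard ratios come from.** The chance that an arm of 126 has no events at 2% is 0.98^126 = 0.078, so the chance for at least one of two arms is 1 − (1 − 0.078)² = 0.15. With 140 per arm it is 1 − (1 − 0.059)² = 0.11. For 10% vs 1.8%, the chance of an empty active arm is 0.982^126 = 0.10, or 0.982^140 = 0.08. A further 10-parameter simulation found treatment infinite in 8–12% of trials at 2%/2%, but in only 1.3% without an empty arm. At 10%/1.8% every such case was an empty arm. The 26% upper figure at 2%/2%, from a 13-parameter model, exceeds what empty arms explain, so the longest list does add some.

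**The case against.** The strongest reply is that a diverging nuisance coefficient does not spoil the treatment hazard ratio. That stands. A reader might infer from 0.4–0.6 events per parameter that the treatment hazard ratio would be unusable. The simulations do not support this: it is finite in most trials even at 2%, and in all or nearly all at 5%/5% and 10%/10%.

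It also stands that an unadjusted Cox model is no cure, because it too is infinite when one arm is empty.

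A reader might extend the point to all four endpoints, or take 2–10% as the expected range. The documents support neither. Creatinine doubling runs to 20%, and 40% eGFR decline is tabulated at 20–60%.

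A rule of 10 events per parameter would be too strict. It needs 90–130 events, and would remove adjustment from 40% eGFR decline at 20%/8% (35 events) and creatinine doubling at 20%/20% (50 events). At about 36–54 simulated events, 0–17% of fits had any infinite coefficient and the treatment coefficient was never infinite.

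The plan already admits low power for these three endpoints, and tenofovir toxicity is not in the secondary endpoint list of Section 1.2. Safety oversight also runs through adverse event reporting and the DSMB. This limits the consequence but does not answer the point: low power means a wide interval, while an infinite coefficient calls for a different model. The chi-squared tests in Appendix B are part of the power calculations and do not override the analysis section.

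**Conclusion.** The point holds for tenofovir toxicity, all-cause mortality and creatinine doubling toward the low end of its range. At 2% the stated model has about 5 events for 9–13 parameters, and more than half of fits contain an infinite coefficient, usually for a nuisance covariate. The treatment hazard ratio is noisier, and it is infinite in roughly 8–26% of trials, mainly because an arm is empty. At 10% vs 1.8% it is infinite in about 10%. With 10% mortality in both arms it stays finite.

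The event counts follow from the plan's own rates. The parameter count rests on the assumed knots and terms. The failure rates also rest on covariate prevalences that the documents do not give, hence the wide ranges. The effect is confined to secondary outcomes that the plan already calls low-powered. It is a gap worth closing, but no threat to the primary analyses.

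**What to change.** In the secondary-analysis paragraph of Section 8.0, limit the full-covariate rule. For tenofovir toxicity, all-cause mortality and creatinine doubling, when the blinded pooled event count is low (for example under about 30), specify a log-rank test plus a Firth-penalised Cox model with treatment and linear log baseline uACR, reported with profile-likelihood intervals. Penalisation keeps the estimate finite when an arm is empty. Keep the full covariate model otherwise, and for 40% eGFR decline throughout. State that the dolutegravir sensitivity analyses follow the same rule.

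Thirty events among 252 patients is a pooled rate of 30/252 = 11.9%. At the plan's rates, mortality (at most 25 events) and tenofovir toxicity (16 even at 2% vs 11%) would therefore use the reduced model, and creatinine doubling could go either way.

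The cost is a short change to the text and less covariate adjustment for the sparse endpoints. The threshold is a convention, so it should be fixed before unblinding, including before the interim efficacy analysis described in Section 6.0.
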